15.7. Appendix 7: Reporting Standards for Missing Data

15.7.1. Premature Withdrawals

| Element | Reporting Detail |
|---------|---|
| General | 
 Participant study completion (i.e. as specified in the protocol) was defined as 
 Randomly assigned to either treatment group, completed the randomized Maintenance Phase including Week 100 and did not enter the Extension Phase; Randomly assigned to either treatment group, completed the randomized Maintenance Phase including Week 100, and entered and completed the Extension Phase (defined as remaining on study until commercial supplies of CAB LA + RPV LA Q4W or Q8W regimen become locally available or development of CAB LA + RPV LA is terminated). 
Participants who withdraw from CAB LA + RPV LA and go into the LTFU Phase, and participants who withdraw from oral lead-in will be considered to have prematurely withdrawn from the study treatment.
 
In addition to the 52-week Follow-Up phase required for participants who receive one or more injections with CAB LA or RPV LA, an in-clinic Follow-Up visit will be conducted approximately 4 weeks after the last dose of study medication for participants who withdraw during the oral lead-in period with ongoing AEs, and serious adverse events (SAEs) and also any laboratory abnormalities that are considered to be AEs or potentially harmful to the participant, at the last on-study visit. Assessments at the Follow-up visit should reflect any ongoing complaints (e.g., blood draws to follow a laboratory abnormality). Follow-Up visits are not required for successful completion of the study.
 
 Withdrawn participants were not replaced in the study. All available data from participants who were withdrawn from the study will be listed and all available planned data will be included in summary tables and figures, unless otherwise specified. Withdrawal visits will be slotted as per Error! Not a valid result for table.: Assessment Windows or will be summarised as withdrawal visits. |

15.7.2. Handling of Missing Data

| Element | Reporting Detail |
|----------|--|
| General | 
 Missing data occurs when any requested data is not provided, leading to blank fields on the collection instrument: 
 These data will be indicated by the use of a “blank” in participant listing displays. Unless all data for a specific visit are missing in which case the data is excluded from the table. Answers such as “Not applicable” and “Not evaluable” are not considered to be missing data and should be displayed as such. |
| Outliers | 
 Any participants excluded from the summaries and/or statistical analyses will be documented along with the reason for exclusion in the clinical study report. |

15.7.2.1. Handling of Missing and Partial Dates

| Element | Reporting Detail |
|--|--|
| General | 
 Partial dates will be displayed as captured in participant listing displays. |
| Adverse Events | 
 The eCRF allows for the possibility of partial dates (i.e., only month and year) to be recorded for AE start and end dates; that is, the day of the month may be missing. In such a case, the following conventions will be applied for calculating the time to onset and the duration of the event: 
 Missing Start Day: First of the month will be used unless this is before the start date of study treatment; in this case the study treatment start date will be used and hence the event is considered On-treatment as per Appendix 4: Study Phases and Treatment State. Missing Stop Day: Last day of the month will be used, unless this is after the last contact date; in this case the last contact date will be used. Completely missing start or end dates will remain missing, with no imputation applied. Consequently, time to onset and duration of such events will be missing. |
| ART/Non-ART Medications or Medical History | 
 Partial dates recorded in the eCRF will be imputed using the following convention: 
 If the partial date is a start date, a '01' will be used for the day and 'Jan' will be used for the month. If the partial date is a stop date, a '28/29/30/31' will be used for the day (dependent on the month and year) and 'Dec' will be used for the month. If medications recorded in the eCRF as prior (e.g. recorded in prior ART or prior ATLAS ART forms), the earlier date of the imputed and the day prior to the maintenance phase treatment start date will be used, i.e. min (imputed stop date, maintenance phase treatment start date - 1). For medications with completely missing start date, they will be considered started prior to the maintenance phase treatment start date. For medications with completely missing stop date, they will be considered ongoing unless recorded in eCRF as prior (e.g. recorded in prior ART or prior ATLAS ART forms). For ART booster medications, the start and stop dates are not recorded in the database (i.e. missing), the dates will be imputed to be the same as the dates of their parent medications. The recorded partial or missing date will be displayed in listings. |
| Health outcomes | 
 For the health outcomes questionnaire data, please refer to Section 12. For the summary of individual item scores outputs, missing scores will not be computed. |

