- Please refer to [Appendix 7](#): Reporting Standards for Missing Data for handling of missing and partial dates for medications. Use the rules in this table if medication date is completely missing.
- [a] The ART medication stopped on start date of Maintenance treatment will be considered a prior medication and will not be considered concomitant during the Maintenance phase. If the stop date of ART medication is completely missing and this medication is recorded in eCRF as prior (e.g. prior ART or prior ATLAS ART forms), it will be considered a prior medication and will not be considered concomitant during the Maintenance phase.
- [b] If subjects have missing LFTU ART start date, only the lower bound will be considered in the derivation.
- [c] Refer to Section [15.6.1](#) for the definition.

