15.4. Appendix 4: Study Phases and Treatment State

15.4.1. Study Phases

Assessments and events will be classified according to the time of occurrence relative to the Treatment Start Date defined in Section 15.6.1.

AEs will be assigned to study phases as defined in Table 17. For example, adverse events on/after start of maintenance phase IP and prior to start of Extension phase IP/LTFU ART will be assigned to the Maintenance Phase.

Laboratory data (efficacy, safety, PK and virology), HIV associated Conditions, health outcomes assessments, vital signs, and ECGs will be assigned to study phases as defined as in Table 18. For example, assessments/events occurring after start of maintenance phase IP and up to and including start of extension phase IP/LTFU ART will be assigned to the Maintenance Phase.

Assessments/events are assigned to study phases sequentially, starting from the top of each table, except for the assessments/events occurring after returning to Extension phase from the sub-study participation. No study phases will be assigned to medications.

Table 17 Assignment of Study Phases for AEs

| Study Phase | Definition |
|-------------|---|
| Screening | Date < Maintenance Treatment Start Date |
| Maintenance | 
For participants continuing into Extension Phase: Maintenance Treatment Start Date ≤ Date < Date of Nominal Week 100 Visit
 
For participants not continuing into Extension Phase: For participants continuing into LTFU Phase: Maintenance Treatment Start Date ≤ Date < LTFU ART Start Date^[a]
 |

| | |
|---------------------|---|

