| Screening | Date ≤ Maintenance Treatment Start Date Note: 2-hour post-dose ECG taken on the Maintenance Treatment Start Date will be excluded. |
| Maintenance | 
For participants continuing into Extension Phase: Maintenance Treatment Start Date < Date ≤ Date of Nominal Week 100 Visit^[a] Note: 2-hour post-dose ECG taken on the Maintenance Treatment Start Date will be included.
 
For participants not continuing into Extension Phase: For participants continuing into LTFU Phase: Maintenance Treatment Start Date < Date ≤ LTFU ART Start Date^[b] For participants transitioned to marketed product/alternative HAART and did not withdraw study due to safety related reason: Maintenance Treatment Start Date < Date ≤ Date of end of study +35 days (Q4W) or + 63 days (Q8W) Note: 2-hour post-dose ECG taken on the Maintenance Treatment Start Date will be included.
 |
| Extension | 
For participants continuing into Extension Phase and not entering the sub-study: If participants continued into LTFU Phase after the Extension phase: Date of Nominal Week 100 Visit^[a] < Date ≤ LTFU ART Start Date^[b] If participants transitioned to marketed product/alternative HAART and did not withdraw study due to safety related reason, then Date of Nominal Week 100 Visit^[a] < Date ≤ Date of end of study +35 days (Q4W) or + 63 days (Q8W)
 
For participants continuing into Extension Phase, entering the sub-study but not returning to Extension Phase: Date of Nominal Week 100 Visit^[a] < Date < Date of First Sub-study Record
 
For participants continuing into Extension Phase, entering the sub-study and returning to Extension Phase: Before the sub-study: Date of Nominal Week 100 Visit^[a] < Date < Date of First Sub-study Record After the sub-study: For participants continuing into LTFU Phase after return to extension phase: End of Sub-study Date^[b] < Date ≤ LTFU ART Start Date^[a] For participants transitioned to marketed product/alternative HAART and did not withdraw study due to safety related reason: End of Sub-study Date^[b] < Date ≤ Date of end of study +35 days (Q4W) or + 63 days (Q8W)
 |

| | |
|-----------------------------|--|

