- [b] If participants have missing LFTU ART start date (i.e. the participants have not started ART in LFTU yet), only the lower bound of the window will be considered in the derivation.
- [c] End of Sub-study Date is defined in Section 15.6.1.
- [d] The post-dose assessments (e.g. 2-hour post-dose ECG, 2-hour post-dose PK and NRS) taken on the date of first thigh injection will be assigned Thigh Injection Phase, instead of Sub-study Screening Phase.
- [e] The Date of Nominal Sub-study Week 16 is defined in Section 15.6.1. The post-dose assessment (e.g. NRS) taken on the date of Sub-study Week 16 injection will be assigned Return to Gluteal Injection Phase, instead of Thigh Injection Phase.

Table 19 Assignment to Long-term Follow-up Phase

| Study Phase | Definition |
|-------------|------------|
|-------------|------------|

| | |
|---------------------|--|
| Long-term Follow-up | Date > max (Last IM Injection Date, Last Oral Bridging End Date) |
|---------------------|--|

- Date = Assessment/Start Date
- For AEs leading to withdrawal and started on the same date as LTFU ART Start Date, appropriate study treatment associated phase, instead of long-term follow-up phase, will be assigned. Refer to [Table 17](#) for details.

Only participants who received at least one CAB and/or RPV injection will enter the long-term follow-up. Participants transitioning to CAB+RPV LA marketed product or alternative HAART (except due to safety-related reasons) do not need to enter the LTFU Phase. Note that the long-term follow-up phase and maintenance/extension/sub-study screening/thigh injection/return to gluteal injection phases are not necessarily mutually exclusive and are to be defined with separate phase variables in the datasets. For example, an Q4W IM participant who has Week 44 injection and withdrawal at Week 48 without receiving Week 48 injection, the “Week 48 withdrawal visit” belongs to both the maintenance phase and long-term follow-up phase.

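### Partial start dates of follow-up ART are imputed with no lower bound, so the date that closes the Maintenance Phase can precede the last study dose or the withdrawal assessment

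*SAP*

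**What the plan says.** Section 15.7.2.1 covers ART, non-ART medications and medical history together: "If the partial date is a start date, a '01' will be used for the day and 'Jan' will be used for the month". The only bound in that row is on stop dates of medications recorded as prior: "min (imputed stop date, maintenance phase treatment start date - 1", closing the bracket. Adverse-event start dates in the same table do have a floor: "First of the month will be used unless this is before the start date of study treatment".

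The note under Table 2 (section 6.2), a table that uses LTFU ART start as a boundary, sends the reader to Appendix 7: "Reporting Standards for Missing Data for handling of missing and partial dates for medications".

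The same date closes the Maintenance Phase in section 15.4.1. Table 18 (laboratory data, including viral load) reads "For participants continuing into LTFU Phase: Maintenance Treatment Start Date < Date ≤ LTFU ART Start Date". Table 17 (adverse events) reads "Maintenance Treatment Start Date ≤ Date < LTFU ART Start Date". Table 20 cuts on-treatment status in LTFU at the earlier of that date and the dosing limit (last injection + 35 days for Q4W or + 63 for Q8W, or last oral dose + 1 if later).

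The only special provision for this date is for one that is absent: "If participants have missing LFTU ART start date (i.e. the participants have not started ART in LFTU yet), only the lower bound" is then used. A date that is present but partial has no rule of its own, and section 15.6.1 does not define LTFU ART Start Date.

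**The concern.** A first-of-month convention does little harm when a date only feeds a medication listing. Here the same date is a phase boundary. The Table 10 notes admit to the Snapshot only viral loads that are on-treatment within the assigned phase. Appendix 9, step 5.2.2.3, makes a non-safety withdrawal a failure only if the last on-treatment value is 50 c/mL or more. Section 7.1.4 says what is intended: a non-adverse-event discontinuation with HIV-1 RNA of 50 c/mL or more at that time counts as HIV-1 RNA of 50 c/mL or more. A date convention should not be able to reverse that classification.

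The rule can also produce an impossible sequence. Follow-up ART belongs after study treatment has stopped, and Table 19 starts LTFU after the last injection or oral bridging dose. The imputed start can nevertheless fall earlier than that.

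**Working it through.** The SAP gives no count of partial LTFU ART dates, so there is no plan figure to reproduce. The check follows one dated example through the rules and then does the calendar arithmetic.

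**Example (illustrative dates, Q4W arm).** Last injection Day 225 (23 May), viral load below 50. Withdrawal for a non-safety reason on Day 253 (20 June), viral load 180. Follow-up ART truly starts on Day 254 (21 June).

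*Complete date.* Table 18: 253 ≤ 254, so the value is in Maintenance. Table 20: 253 ≤ 225 + 35 = 260, so it is on-treatment. Day 253 lies before the Week 48 window (Days 295 to 378), so step 5.2.2.3 applies. The last on-treatment value is 180, and the result is HIV-1 RNA ≥ 50.

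*Month and year only.* The start becomes 1 June = Day 234.
- Table 18: 253 > 234, so the value is outside Maintenance.
- Table 20, LTFU: min(234, 260) = 234, and 253 > 234, so it is post-treatment there too.
- The last usable value is the one below 50, and the result is no virologic data.

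*Year only.* The start becomes 1 January = Day 83, which is 142 days before the last injection. Adverse events from Day 83 to Day 225 are not in Maintenance (Table 17 needs a date before Day 83) and not in LTFU (Table 19 needs a date after Day 225). Viral loads from Day 84 to Day 225 leave Maintenance as well.

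**How far dates move.** Assume the true start is uniform over a 365-day year. The backward shift averages 14.7 days (maximum 30) if the day is missing, and 182 days (maximum 364) if day and month are missing.

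**How often a withdrawal sample is displaced, given a partial date.** Let the sample precede ART by g days. With the day missing, the sample is displaced when the true start falls on day g + 2 of its month or later. For g up to 27 the share is (365 − 12(g + 1))/365. At g = 28 only the 18 dates that are the 30th or 31st count. With day and month missing, the share is (364 − g)/365.

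| g (days) | Day missing | Day and month missing |
|---|---|---|
| 0 | 353/365 = 97% | 364/365 = 99.7% |
| 7 | 269/365 = 74% | 357/365 = 98% |
| 14 | 185/365 = 51% | 350/365 = 96% |
| 28 | 18/365 = 5% | 336/365 = 92% |

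The gap g is an assumption; the SAP says nothing about it.

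**Weight in the primary analysis.** One reclassified participant moves an arm's proportion by 1/510 = 0.196 percentage points. Take the SAP's Sato interval in a single stratum, with an assumed 10 failures of 510 on Q4W. Then 20 failures on Q8W give an upper limit of 4.03%, and 19 give 3.80%. One record matters only if the result lies at the 4% margin.

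**The case against.** The strongest reply has five parts.

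1. *The link is inferred.* Section 15.7.2.1 is a general convention, and Tables 17 and 18 do not cite it. That is fair, but Table 2 does send medication dates there, the boundary is an ART start date, and no other rule is offered. A programmer would apply this one.

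2. *The order of sample then ART is assumed.* This stands. The Table 14 footnote records that under protocol amendment 1 participants had no withdrawal visit and went straight to LTFU Month 1. Excluding viral loads possibly affected by new ART is also reasonable, so forcing every withdrawal sample to precede ART would bring its own error.

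3. *The direction is open.* This stands. A reader might infer that the rule hides failures and so favours non-inferiority. The SAP does not support that: Appendix 9 classes a permanent ART change before the timepoint as HIV-1 RNA ≥ 50, and that condition is tested first, so an imputed start before the last dose could create a failure. Both arms share the rule. Reading that condition to cover all ART after discontinuation would prevent lost failures, but would leave the suppressed-withdrawal row of step 5.2.2.3 almost empty.

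4. *Several conditions must coincide.* This stands. The effect needs a partial date, a non-safety withdrawal, no usable value in the window, a sample after the imputed date, and no remaining last value of 50 or more. The percentages above apply only once a partial date exists.

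5. *Adverse events are moved, not lost, and the confirmed virologic failure (CVF) definition is elsewhere.* Events after the last injection do stay in LTFU. Only those between an imputed date and a later last injection have no phase, and they still appear in listings without phase restriction. Section 15.6.3 leaves the CVF definition to the protocol, so no effect on CVF is claimed.

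**Conclusion.** The point holds as a defect in a derivation rule. Applied as written, the rule can place follow-up ART before the last study dose or the withdrawal assessment. Viral loads that belong to study treatment then leave the Snapshot data, and some adverse events are left without a phase. The primary endpoint can be misclassified in either direction.

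The size is unknown and probably small: 0.196 percentage points per participant at 510 per arm, with no count of partial dates in the SAP. The conclusion rests on section 15.7.2.1 applying to LTFU ART Start Date, which is the natural reading but is not stated. The documents do not show that the primary result is biased towards non-inferiority, or that any particular number of failures is lost.

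**What to change.** In section 15.7.2.1, add a rule for ART begun after permanent discontinuation. A partial start date is imputed as the later of (a) the 01 or 01-Jan date and (b) the day after the last dose of study treatment (injection or oral bridging), but not beyond the end of the recorded month or year. State that this is the LTFU ART Start Date used in Tables 17, 18 and 20 and in Appendices 9 and 10.

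In the year-only example this moves the start from Day 83 to Day 226, which closes the adverse-event gap and restores the viral loads up to the last injection. It does not settle the Day 253 sample, because the imputed start (Day 234 or Day 226) still precedes it. So where a withdrawal viral load falls between the imputed date and the end of the recorded month or year, query the date. If it stays unresolved, report a sensitivity Snapshot analysis that treats the sample as taken before ART.

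The cost is a short addition to the text, a small program change, re-derivation of a few records, and one sensitivity run. Section 5.4.2 speaks of the Week 48 data cut as past, so any change to a Week 48 classification should be reported openly as a re-derivation.

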15.7.2.2. Handling of Missing data for Statistical Analysis

| Element | Reporting Detail |
|------------|---|
| Snapshot | 
 In the Snapshot dataset, participants without HIV-1 RNA data in the assessment window for the visit of interest (due to missing data or discontinuation of IP prior to the visit window) do not belong to 'HIV-1 RNA < 50 c/mL (or <200 c/mL)'. The nature of this missing data will be further classified in Snapshot summaries as either 'HIV-1 RNA ≥ 50 c/mL' (or "HIV-1 RNA ≥ 200 c/mL") or 'No Virologic Data at Week X'; Appendix 9: Snapshot Algorithm Details for full details |
| LOCF | 
 In the LOCF dataset, missing values will be carried forward from the previous, non-missing available on-treatment assessment. If the baseline value is missing any missing values until the first non-missing value will remain missing. |
| Lipid LOCF | 
Baseline for Lipids LOCF Analyses in main study:
 
 Last evaluable lipids assessment up to and including the start of IP, where 'evaluable' is defined as: Lipid-modifying agents not taken within 12 weeks of the date of assessment and Lipids are collected in a fasting state. 
During the Maintenance or Extension Phase:
 
 If participants initiate serum lipid-modifying agents during the Maintenance or Extension Phase, then the last available fasted on-treatment lipid values prior to the initiation will be used in place of future, observed on-treatment values. Imputation at planned visits will continue even if the participant discontinues the lipid-modifying agent. Missing assessments will not be imputed if there is no last available fasting on-treatment lipid value prior to the initiation of serum lipid-modifying agent. If participants take lipid modifying agents within 12 weeks prior to the start of the study treatment, all the post-baseline values will be missing. 
Baseline for Lipids LOCF Analyses in sub-study:
 
 Last evaluable lipids assessment up to and including the start of thigh injection, where 'evaluable' is defined as: Lipid-modifying agents not taken within 12 weeks of the date of assessment and Lipids are collected in a fasting state. 
During the Thigh Injection or Return to Gluteal Injection Phase:
 
 If participants initiate serum lipid-modifying agents during the Thigh injection or Return to Gluteal Injection Phase, then the last available fasted on-treatment lipid values prior to the initiation will be used in place of future, observed on-treatment values in sub-study. Imputation at planned visits will continue even if the participant discontinues the lipid-modifying agent. Missing assessments will not be imputed if there is no last available fasting on-treatment lipid value prior to the initiation of serum lipid-modifying agent. If participants take lipid modifying agents within 12 weeks prior to the start of the thigh injection, all the post-baseline values in sub-study will be missing. 
Analyses Evaluated with Lipid LOCF Dataset:
 |

| Element | Reporting Detail |
|---------|--|
| | 
Week 48 analysis:
 
This dataset will be used to summarize fasting lipids parameters in the following displays:
 
Summary of Fasting TC/HDL ratio Change from Baseline Summary of Fasting Lipids Percentage Changes from Baseline Summary of Chemistry Changes from Baseline Summary of Chemistry Values
 
All other displays of lipids (e.g. toxicity tables and NCEP tables) will use observed fasting data, without LOCF imputation.
 
Post-Week 48 analysis:
 
Lipid LOCF dataset will be used for all lipid analysis except for the Summary of Maximum Post-Baseline Emergent Chemistry Toxicities.
 |

